15 tools include Patient Buddy to prevent avoidable readmissions and EncephalApp Stroop to detect and guide therapy for cognitive dysfunction  
16 in cirrhosis. However the evaluation of these tools in a multi-center study that adapts to the status of the patients and their caregivers is required.  
17

18 The central hypothesis is that cirrhotic patients randomized to health IT interventions that elicit PROs in a structured outpatient setting will have  
19 a significantly greater reduction in hospital readmissions because of improved communication with their medical teams compared to standard  
20 of care regardless of scheduled return outpatient visits.

21 Patient Buddy™ is an innovative application that is HIPAA compliant and adaptable to specific patient populations. It includes the ability to  
22 securely integrate with hospital based systems or work in a HIPAA compliant hosted environment with separate patient and caregiver interfaces  
23 focused on several aspects that impact re-hospitalization. Specifically, it has the ability to record vitals, cognitive performance, questionnaires,  
24 medication dosages and intake and can communicate with the clinicians and pharmacies. Patient Buddy has been developed by our technology  
25 partner, Creative Information Technology, Inc. (CITI).

26 Given this immense gap in our knowledge regarding the use of patient and caregiver-centered interfaces in the prevention of re-hospitalization,  
27 our hypothesis is that Patient Buddy, a mobile patient-caregiver-clinician interface, will effectively reduce readmissions in decompensated  
28 cirrhotic patients within 30 days of discharge.

29 We plan to follow three groups of cirrhotic patients from the time  
30 of hospital dismissal randomly divided into either receiving standard of care, using devices through which they can communicate with the clinical  
31 teams and using devices and structured follow-up over thirty days. Our aim is to develop these devices so as to learn quickly about issues that  
32 patients and their caregivers are facing so that we can intervene to stop unnecessary and re-hospitalizations in this population.

33 **2. Describe the study's specific aims or goals.**

34 **Specific Aim 1: To evaluate in a multi-center, randomized trial the effectiveness of (patient reported outcomes) PROs elicited using  
35 PatientBuddy and EncephalApp Stroop with and without scheduled outpatients return visits on the prevention of avoidable 30 day  
36 readmissions in patients with cirrhosis and their caregivers compared to standard of care.**

37  
38 As part of this specific aim, we will include 450 total cirrhotic patients and 450 caregivers (150 patients and 150 caregivers per center), who will  
39 be followed for 30 days post-discharge. The groups will be randomized 1:1:1 into a standard  
40 of care group, a group receiving health IT interventions who will receive PatientBuddy and EncephalApp Stroop with as-needed follow-up and  
41 another group that receives the same health IT interventions along with scheduled outpatient visits and calls within 30 days of discharge.  
42 Avoidable readmissions will be adjudged using a blinded adjudication committee and the differences between the three groups will be compared.  
43

44 The Health IT groups will be given iPhones loaded with the Patient Buddy app with caregiver and patient interfaces. They will be instructed  
45 extensively regarding the use of the App, which is preloaded with variables that associated with readmissions such as medications and  
46 adherence, issues with cognition and orientation and new symptoms. The patient and the caregiver will have separate devices linked to a device  
47 with the nurse coordinator through which daily communication will occur between patient/caregivers and the study team regarding previously  
48 identified risk factors associated with readmission. With this enhanced communication and educational value of the App, the study team will  
49 have greater access to events at patients' homes and the potential to prevent readmissions by intervening at that stage. The team will also  
50 engage the end-users (patients, caregivers and the nurse coordinator) by inquiring about their input in order to enhance the interface, user-  
51 friendliness and impact of the App. A detailed analysis of 30-day readmissions, including potential preventability with Patient Buddy will be  
52 performed. CITI will be responsible for establishing and monitoring the communication channels and implementation of the interfaces.  
53  
54  
55  
56  
57  
58  
59  
60

1 **Specific aim 2: To incorporate the opinion of key stakeholders (patients, caregivers and nurse coordinators) towards improving the**  
2 **Patient Buddy App in the prevention of readmission in cirrhosis**

3 The input of patients, caregivers and nurse coordinator and analysis of potential preventability of readmissions in specific aim 1 will be used  
4 to enhance the Patient Buddy App.

5 **6.3. Describe the study's background and significance, including citations, or upload a citation list in document upload. Use lay  
7 language whenever possible.**

8 1. Significance of the problem of cirrhosis and hospitalization

9 Cirrhosis affects more than 5 million patients in the United States. The natural history of cirrhosis involves a compensated and a  
10 decompensated phase. Decompensated patients develop complications of cirrhosis such as hepatic encephalopathy (HE), ascites, variceal  
11 bleeding, infections and spontaneous bacterial peritonitis (SBP). These complications led to more than 1.5 million hospitalizations and cost  
12 nearly \$4 billion yearly.

13 2. Readmissions in cirrhotic patients are an unresolved burden

14 15 Despite readmissions within 30 days being a quality improvement issue, there have been several federally-funded studies that have shown a  
16 relentless increase in this rate. The 30-day readmission rate for cirrhotic patients is as high as 37% in prior NIH- sponsored studies from  
17 multiple centers in North America. This was associated with a significantly higher 90-day mortality compared to subjects free of 30-day  
18 readmission. Therefore readmissions are an unresolved burden on the patients and the medical system.

19 3. Factors associated with readmission can potentially be modified

20 Studies from our group and several other groups have demonstrated that specific cirrhotic subgroups are particularly vulnerable to  
21 readmission. A large proportion of these factors are modifiable with poly-pharmacy, lack of understanding of medication use and their  
22 adverse events being primary issues. Patients are often re-admitted for HE, falls, infections and ascites-related issues. However despite  
23 the knowledge, there is poor dissemination of these findings into practice in order to prevent readmissions.

24 4. Caregiver engagement in the prevention of readmission is poorly studied in cirrhosis

25 Since most studies have concentrated on the individual patients' understanding of their disease process and their medications, the role of the  
26 caregiver/companion during this process has not been well studied. The involvement of the caregiver is a critical piece of the puzzle because  
27 patients with decompensated cirrhosis have cognitive dysfunction due to minimal or overt HE that can impair judgment and memory and are  
28 often unable to perform instrumental activities of daily living. This can impact their daily function, development of future complications and  
29 socio-economic status from an individual, family and societal basis. Therefore, caregivers are essential to the understanding of the  
30 disease complications, prevention of medication-associated issues and to alerting relevant clinicians earlier to manage problems as an  
31 outpatient, which if neglected could lead to readmission. Studies have shown that caregivers of cirrhotic patients are deeply affected by this  
32 disease from a psychosocial and financial perspective but they are often not involved while the disease severity, progression and complications  
33 are being explained to the patients.

34 The absence of caregiver involvement in the previous studies of readmission prevention is a major gap in our knowledge which requires  
35 investigation.

36 5. Current methods of preventing readmissions are inadequate and are reactive instead of pro-active

37 The current standard of care in cirrhosis at this time is to schedule appointment follow-up and occasional telephone calls to the patients  
38 directly. There is little systematic investment into engaging the patient/caregiver dyad proactively and disseminating knowledge. The system  
39 thus is only geared towards evaluating patients when the problem requires emergent or urgent visits. Therefore current knowledge that  
40 could prevent these readmissions is inadequately disseminated to the affected parties with the current standard of care.

41 6. Mobile health applications are required to engage patients and caregivers with clinicians

42 44 The rapid dissemination of multiple studies that clearly define preventable reasons for readmissions in cirrhosis requires direct modes of  
43 communication between clinicians and the patient/caregiver dyads. Mobile health apps which are able to communicate problems that can  
44 be handled before they need an emergent visit to the hospital are therefore a potential method to prevent these readmissions.

45 48 The conclusion from the original proof-of-concept study : "patient buddy app for prevention of readmissions in cirrhosis patients", showed that  
46 the use of the Patient Buddy app is feasible in recently discharged patients with cirrhosis and their caregivers. Eight HE-related readmissions  
47 were potentially avoided after the use of the App. (Note abstract uploaded in documents section) Standard of care follow-up post discharge is  
48 4 weeks (30 days) minimum and possibly 2 weeks depending on the reason for admission, based on the results of our pilot study. Since we  
49 noted poor adherence with the fall -risk assessment and daily sodium intake in the previous pilot version of the Buddy App Study, both have  
50 been removed in the RCT version of this study."

51

52

53

54

55

56

[figure not shown]
57

58

59

60

1  
2 4. \* Describe the proposed research (Figure below is the flow chart for the study design)

**Recruitment of Subjects and Informed Consent Process:** Subjects will be recruited from the Inpatient Service at VAMC. Each morning, the CITI-trained nurse coordinator (who will also act as the nurse coordinator) will check with the inpatient attending if cirrhotic subjects have been admitted. These subjects will be reviewed by the PI and/or co-investigators. If they appear to be reasonable candidates, the coordinator and investigators will discuss the study with them and their caregivers. Sufficient opportunity will be provided to them to have all their questions/concerns answered before consent will be obtained. If subjects and caregivers are agreeable, study activities will start at the day of discharge. All female patients of reproductive age group will undergo a urine pregnancy test.

After informed consent is obtained from both patient and the caregiver separately, we will administer the EncephalApp Stroop to the patient. EncephalApp Stroop is a validated cognitive test that takes 5-10 minutes to perform, which can give valuable information regarding the cognitive flexibility and psychomotor speed of the participant. This has an easier Off State and a more difficult On state. The ultimate outcome is the time taken to complete both Off and On states in seconds known as OffTime+OnTime. The EncephalApp Stroop will be administered by the study team to patients at baseline and at study end in group 1. For those randomized to group 2, it will be administered at baseline to the patient by the study team and then will be taught to the caregiver to administer weekly or if the subject has any issues. Like in group 1, all patients will undergo this again at study end.

Training will be given to all patients and caregivers regarding

(a) cirrhosis (b) hepatic encephalopathy (c) ascites and low-sodium diet and (d) individual medication evaluation, using printed standardized patient information handouts from UptoDate. We will answer all questions raised by the patients and caregivers and the team will also individualize training based on the specific reason for admission.

We will then proceed with 1:1:1 site-specific randomization in blocks of 4 using a random number generator overseen by the statistician that will be communicated to the sites beforehand.

48

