**41. \* Provide justification for the sample size:**

42 Sample size: Prior studies and our cohort have shown a 30-day readmission rate around 33% using current practice, and of which 20% were  
43 considered avoidable. Per our preliminary data, the rate of 30-day avoidable readmission reduced to 5%. However, we will be circumspect  
44 and increase this relative avoidable readmission rate to 9%. In order to determine a similar reduction at 80% power at an  $\alpha = 0.05$  level of  
45 significance we would require 45 patients in the Health-IT+scheduled visits, 45 patients in the Health- IT only and 45 patients in the standard  
46 of care group per site leading to a total of 135 patients per site or 405 total patients. This will also include 405 caregivers. Allowing for a 10%  
47 dropout rate, we plan to we will enroll a total of 450 patients, of which 150 will be randomized to health-IT+scheduled visits, 150 to health-IT  
48 only and 150 to standard of care across all three sites. This will be accompanied by an equal number of the respective caregivers bringing the  
49 grand total of subjects across all three sites to 900.

50 Therefore at McGuire VAMC we will enroll 50 patients and 50 caregivers in each group for a total of 300 subjects (150 patients and  
50 caregivers).

51

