12 Justification: To increase generalizability  
13

14 **Protocol Amendment 2**  
15

16 Due to COVID-19 related gap in enrollment, funding shortfalls, and low likelihood of us reaching the  
17 original study goals, a re-evaluation of the data was done to see if we could combine the two health-IT  
18 groups. Avoidable readmissions were similar across the 2 health IT groups and therefore, instead of 1:1:1  
19 randomization, this was changed to 1:1 randomization with a total of 464 subjects ( 232 patients and 232  
20 caregivers).  
21

22 Justification: reduced enrolment requiring combination of the groups.  
23

24  
25  
26  
27  
28  
29  
30  
31  
32  
33  
34  
35  
36  
37  
38  
39  
40  
41  
42  
43  
44  
45  
46  
47  
48  
49  
50  
51  
52  
53  
54  
55  
56  
57  
58  
59

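### A 1:1:1 allocation cannot be balanced in blocks of 4: the three-arm rule cannot be carried out as written, and the block composition actually used must be stated

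*Combined protocol and SAP*

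**What the plan says.** Under item 4 (proposed research), the paragraph just before the Group 1 description reads: "We will then proceed with 1:1:1 site-specific randomization in blocks of 4". The sentence goes on to say how the list is made: "using a random number generator overseen by the statistician that will be communicated to the sites beforehand". It does not describe what a block contains.

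The equal three-way split is repeated elsewhere. Specific Aim 1 states: "The groups will be randomized 1:1:1 into a standard" of care group and two health-IT groups, with "150 patients and 150 caregivers per center". The sample size justification plans 150 patients in each group overall and says of one site: "Therefore at McGuire VAMC we will enroll 50 patients and 50 caregivers in each group for a total of 300 subjects".

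Protocol Amendment 2, at the end of the document, combines the two health-IT groups. It records the move away from 1:1:1 in these words: "randomization, this was changed to 1:1 randomization with a total of 464 subjects", of whom 232 are patients. It gives no block size for the 1:1 stage.

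**The concern.** A permuted block keeps a stated ratio only if its size is a multiple of the sum of the ratio's terms. For 1:1:1 that sum is 3, and 4 is not a multiple of 3. Anyone generating lists from this text has to depart from it: double one arm in each block, read 4 as four places per arm, or use another block size. The documents do not say which was done, so the lists cannot be reproduced or audited from the protocol.

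Two things are at stake. The first is balance within site, which is the purpose of blocking by site. The second is what happened to the control share when Amendment 2 changed the ratio. It is nominally 1/3 before the change and 1/2 after. If the lists always doubled control, it was already 1/2; if they always doubled a health-IT arm, it was 1/4. Enrolment ran across a COVID-19 gap, so a reader needs to know the ratio in each stage.

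This is separate from allocation concealment. The rule would need correcting even if the lists were fully concealed.

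**Working it through.** **The plan's own figures.** The inputs are from the sample size justification: 45 evaluable patients per group per site, three groups, three sites, 10% dropout.

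- 45 × 3 = 135 per site
- 135 × 3 = 405 in total
- 405 / 0.90 = 450 enrolled
- 450 / (3 sites × 3 groups) = 50 per group per site

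The target of 50 reproduces exactly. It is stated only for the VAMC. At the other sites it follows from 150 patients per center and 1:1:1.

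**Can a block of 4 hold 1:1:1?** 4 / 3 leaves a remainder of 1. Four places can be divided among three arms in C(6,2) = 15 ways. None is equal, and the closest is 2:1:1.

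**Do blocks of 4 fit a site of 150?** 150 / 4 = 37.5, so complete blocks end at 148 or 152 and the last one is cut.

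**What each possible composition gives at a site of 150:**

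| Composition (none is stated) | Result |
|---|---|
| Doubled arm rotates | 50/49/49 after 148; balanced after every 12 patients; exactly 50/50/50 in 1/3 of lists |
| Doubled arm drawn at random in each block | Mean 50 per arm, SD about 2.9; exactly 50/50/50 in about 2% of lists; largest-minus-smallest gap of 5 or more in about 67% |
| Same arm always doubled | 74/37/37 after 148; real ratio 2:1:1 |
| 4 read as four places per arm (block of 12) | 48/48/48 after 144, then half a block |

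- *Rotating arm.* After 148 patients one arm is at 50 and the others at 49. The cut block doubles one of the two lower arms. Its first two places must hold one of each lower arm, which is (2 × 1) of C(4,2) = 6 pairs, or 1/3.
- *Random arm.* The 37 complete blocks contribute a variance of 37 × (1/3) × (2/3) = 8.22, an SD of 2.87. The two places in the cut block bring it to 2.92. The 2% and 67% come from simulating 100,000 site lists.

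**Health-IT to control when the same arm is always doubled.** If control is doubled: (1 + 1):2 = 1:1. If a health-IT arm is doubled: (2 + 1):1 = 3:1. The nominal ratio is 2:1.

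**Precision in that scenario only,** scaled to the original 450 patients, so 225/112.5/112.5 against 150/150/150. The variance factor is the sum of 1/n over the two sides compared.

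- Undoubled against undoubled: 2/112.5 = 0.0178 against 2/150 = 0.0133, 33% larger.
- Doubled against undoubled: 1/225 + 1/112.5 = 0.0133, unchanged.
- Pooled health-IT against control, nominal: 1/300 + 1/150 = 0.0100. With control doubled: 2/225 = 0.0089, which is smaller. With a health-IT arm doubled: 1/337.5 + 1/112.5 = 0.01185, 18.5% larger.

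**Sizes that do fit.** 150 / 3 = 50 complete blocks, and 150 / 6 = 25. Each gives exactly 50/50/50, as does a mixture of 3s and 6s that sums to 150. For the 1:1 stage a block of 4 works, since 4 = 2 + 2.

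**The case against.** The strongest reply is that the intent is not in doubt and the practical effect is probably small. Every statement of the three-arm design says 1:1:1 or equal groups. A competent statistician would have rotated or randomised the fourth place, and either choice gives 1:1:1 over 12 patients or in expectation. A split of 53 against 47 raises the two-arm variance by only about 0.4% (1/53 + 1/47 = 0.04014 against 2/50 = 0.04000). Assignment stays random under any of these compositions, so unequal blocks alone do not bias a comparison within a stage, and such a comparison can use the observed counts. The 50 per group is an enrolment target; the protocol never says that blocking secures it. Amendment 2 has in any case ended three-arm allocation and cut the plan to 232 patients.

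Most of this stands, and it limits the point. A reader might infer that the lists could not have produced 50 per group, that the trial's ratio is unknown, or that a third of the precision was lost. The documents support none of these. Some compositions can reach 50/50/50. The intended ratio is known; what is missing is the block composition. The 33% needs the same arm doubled in every block at every site and then applies only between the two undoubled arms, on a 450-patient base that has been superseded.

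The reply does not rescue the rule itself. It is internally impossible, and the reassuring compositions are guesses, since none is described.

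**Conclusion.** The concern holds as a defect in the stated randomisation rule. No block of 4 can be balanced 1:1:1, and blocking as written cannot guarantee 50 per group at the VAMC or, by implication, at the other sites. That conclusion needs no assumption.

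The size of the effect does rest on an assumption, because the composition is not given. It ranges from negligible (rotating arm), through modest site-level imbalance (random arm), to a real ratio of 2:1:1 (fixed arm). Nothing in the documents indicates that the fixed-arm case occurred. The per-site figures assume the original 150 patients per site, which was not the final plan, so they illustrate the mechanism and do not describe the trial as run.

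No bias and no loss of power has been shown. What is established is that the ratio the three-arm lists actually used, and the block size after the change to 1:1, cannot be determined from the documents.

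**What to change.** 1. In the randomisation paragraph under item 4, replace the block size for the three-arm stage with multiples of 3, for example 3 and 6 mixed within site. State that even block sizes apply only to the 1:1 stage under Amendment 2.
2. Because three-arm allocation has been replaced, have the statistician check the lists already issued. State the block composition actually used before the change and the block size used after it. If the issued lists differ from the corrected rule, record what was done.
3. Report the allocation ratio and the arm counts by site and by stage. Use the actual three-arm ratio wherever 1:1:1 is relied on.

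The cost is a line or so of protocol text, a check of existing lists and one table. New lists would be needed only if any three-arm allocation remained. No extra patients or staff are required.

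### Randomisation is by site and the allocation ratio changed at Amendment 2, but no analysis that accounts for site or allocation period is named

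*Combined protocol and SAP*

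**What the plan says.** The section describing the proposed research sets the allocation: "We will then proceed with 1:1:1 site-specific randomization in blocks of 4 using a random number generator overseen by the statistician". Specific Aim 1 plans three centres, with "150 patients and 150 caregivers per center", and contains the only statement on how the main endpoint is analysed: "Avoidable readmissions will be adjudged using a blinded adjudication committee and the differences between the three groups will be compared". No test, model, effect measure or covariate is given there. The sample size justification gives event rates, significance level, power and numbers, but names no test.

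Protocol Amendment 2 combines the two health-IT groups, changes the ratio to 1:1 and sets the total at 232 patients and 232 caregivers. It gives no analysis method, and does not say how many patients each site had enrolled under the old ratio.

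Two other places bear on whether sites might differ. The description of Group 1 leaves discharge to local hospital policy. The section on avoidable readmissions gives the classification to one committee, with a hepatologist from each of the three sites.

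**The concern.** A trial that restricts randomisation by a factor would normally carry that factor into the analysis. Two things are at stake.

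The first is precision. When arms are balanced within sites, an analysis that ignores site leaves between-site variation in the error term. The standard error is then somewhat too large and the test somewhat conservative, to a degree that depends on how far sites differ.

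The second is bias, and it comes from Amendment 2. Once the health-IT arms are pooled, the expected control share is 1/3 before the amendment and 1/2 after it. If one site did most of its enrolment early and another late, control patients are drawn disproportionately from the late site. Any difference in readmission rate between those sites then appears as a treatment effect. A change in readmission rates over time acts in the same way, even if sites enrolled alike.

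**Working it through.** **Inputs from the plan.** Three sites; control rate 20% and health-IT rate 9% (relative effect 9/20 = 0.45); 45 per group per site, so 135 per group; alpha 0.05 (two-sided assumed) and 80% power; 232 patients after Amendment 2. The plan gives no site rates, so those below are assumed.

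**The plan's own figure.** The sizing ends in "of care group per site leading to a total of 135 patients per site or 405 total patients". A two-sided pairwise comparison of 20% with 9% needs 160 per group, and 135 gives 73% power. A three-group chi-square test (2 df) with 20/9/9% needs 133 per group and has 80.9% power at 135, so it comes within 2 of the stated number. That test is inferred, not stated. Dropout: 405/(1 − 0.10) = 450, as in the plan. Neither calculation contains a site term.

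**Precision, arms balanced within three equal sites.**
- Unadjusted: SE = √{[p0(1−p0) + p1(1−p1)]/n} = √{(0.16 + 0.0819)/135} = 0.0423.
- Stratified: SE = √{(1/9) Σ [p0k(1−p0k) + p1k(1−p1k)]/(n/3)}. For control rates of 10/20/30% and health-IT rates of 4.5/9/13.5%, the three bracketed terms are 0.1330, 0.2419 and 0.3268, summing to 0.7017. Then √{0.7017/(9 × 45)} = 0.0416.

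| Assumed control rates | SE unadjusted | SE stratified | Overstated by | Simulated power, unadjusted vs CMH, 39 per arm per site | Type I error, unadjusted |
|---|---|---|---|---|---|
| 20/20/20% | 0.0423 | 0.0423 | 0% | 67.7% vs 67.7% | 5.0% |
| 15/20/25% | 0.0423 | 0.0421 | 0.4% | 68.1% vs 68.4% | 4.9% |
| 10/20/30% | 0.0423 | 0.0416 | 1.7% | 68.3% vs 69.3% | 4.6% |
| 5/20/35% | 0.0423 | 0.0407 | 4.0% | 68.1% vs 70.4% | 4.0% |

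The SE columns use 135 per group; the percentages are the same at the Amendment 2 size. The last two columns use 39 per arm per site (234 patients, against 232 planned), with 100,000 simulated trials per scenario. The stratified test stays at about 5.0% type I error throughout.

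**Bias after Amendment 2.** Assume equal sites, site rates of 10/20/30%, no treatment effect, and control shares of 1/3, 5/12 and 1/2 (one site enrolling wholly before the amendment, one half and half, one wholly after).
- Control: (1/3 × 0.10 + 5/12 × 0.20 + 1/2 × 0.30)/(1/3 + 5/12 + 1/2) = 0.2667/1.25 = 21.3%.
- Health-IT: (2/3 × 0.10 + 7/12 × 0.20 + 1/2 × 0.30)/(2/3 + 7/12 + 1/2) = 0.3333/1.75 = 19.0%.
- False difference: 2.3 points in favour of health-IT. Simulated type I error of the unadjusted test is just under 7%, against 5.0% for CMH by site.
- With site rates reversed (30/20/10%), the figures are 18.7% and 21.0%, a false difference of 2.3 points against health-IT. If the planned effect is real, unadjusted power is then about 56%, against 67% for CMH.

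**Price of stratifying when sites do not differ.** Keep the same control shares with 78 patients per site: controls 26 + 32.5 + 39 = 97.5, health-IT 52 + 45.5 + 39 = 136.5. The unadjusted SE is √(0.16/97.5 + 0.0819/136.5) = 0.0473. With Mantel-Haenszel weights (n0·n1/N per stratum) it is 0.0477 by site and 0.0480 by site and period. Power, Φ(0.11/SE − 1.96), is 64.2%, 63.4% and 63.1%, a loss of about 1 point.

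**The case against.** A reader might infer that the plan commits to a crude comparison. It does not: it says that groups will be compared and leaves the method open. The gap is an unnamed analysis, not a wrong one.

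A reader might also take it as fact that the standard error is overstated. That depends on between-site differences for which the documents give no figures. Local discharge policy shows that care may vary, not that outcome rates do, and a single committee classifies avoidability. With equal site rates the loss is nil. The largest figure needs a sevenfold spread of control rates over three sites, which nothing in the documents supports.

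Nor is the balance behind the precision argument assured. Under "1:1:1 site-specific randomization in blocks of 4", complete blocks cannot hold three arms equally, because 4 is not a multiple of 3. With simple 1:1 allocation within site, simulated type I error of the unadjusted test is 5.0% in every scenario, so the supposed conservatism disappears.

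All of this stands, and it limits the precision argument to a small, conditional one. It does not remove the need to adjust. Uneven arms within sites are themselves a reason to adjust, and the change of ratio raises the possibility of bias. For the same reason, the comforting inference that ignoring site could only make the test conservative is not supported: in the amended trial the error can go either way.

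**Conclusion.** The point holds in this form: site-specific randomisation and a mid-trial change of ratio are not matched by any named analysis that accounts for them.

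The precision cost of ignoring site is modest: 0% to about 4% of the standard error and 0 to about 2 points of power. This assumes balance within site and control rates from equal to 5/20/35%. The bias could matter more, at 2.3 points in the example against a planned difference of 11 points. It requires that patients from both periods are pooled, as the amended total suggests, that sites enrolled differently across the amendment, and that their readmission rates differ. The documents neither confirm nor exclude the last two. The recommendation rests on cheap protection, not on demonstrated harm. It is worth making because power at the amended size is already only about 68% in these simulations.

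**What to change.** State the primary comparison as health-IT (both arms combined) against standard of care, by a Cochran-Mantel-Haenszel test stratified by site and by allocation period (before or after Amendment 2). Report the Mantel-Haenszel risk difference with its 95% confidence interval, and keep the unadjusted comparison as supportive only. A table of patients by site, period and arm would show whether allocation did vary.

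This takes one or two sentences in the analysis plan. Site and date of randomisation are already held, so nothing new is collected. Power is essentially unchanged if sites do not differ and arms are balanced, and about 1 point lower if sites do not differ and allocation is uneven across strata.
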